Appendix A: Static PHYSICIANS GLOBAL ASSESSMENT PSORIASIS

0. Clear: no signs of psoriasis (Hyper/hypopigmentation changes alone are acceptable). Plaque elevation = 0. Scaling = 0. Erythema = +/- (hyperpigmentation, pigmented macules, diffuse faint pink or red coloration).

1. Almost Clear: Plaque elevation = +/- (possible but difficult to ascertain whether there is slight elevation above normal skin). Scaling = +/- (surface dryness with some white discoloration). Erythema = up to moderate (up to definite red coloration).

2. Mild: Plaque elevation = slight (slight but definite elevation, typically edges are indistinct or sloped). Scaling = fine (fine scale partially or mostly covering lesions). Erythema = up to moderate (up to definite red coloration).

3. Moderate: Plaque elevation = moderate (moderate elevation with rough or sloped, edges). Scaling = coarse (coarse scale covering most or all of the lesions). Erythema = moderate (definite red coloration).

4.Severe: Plaque elevation = marked (marked elevation typically with hard or sharp edges). Scaling = coarse (coarse, nontenacious scale predominates, covering most of all lesions). Erythema = severe (very bright red coloration).

5. Very Severe: Plaque elevation = very marked (very marked elevation typically with hard, sharp edges). Scaling = very coarse (coarse, thick, tenacious scale over most of all lesions; rough surface). Erythema = very severe (extreme red coloration; dusky to deep red coloration).

Source: Walsh, 2013.

.....

1

Appendix B:PSORIATIC BODY SURFACE AREA

		· · · · · · · · · · · · · · · · · · ·		
BODY AREA	% of BODY AREA AFFECTED	% of TOTAL BODY SURFACE AREA	% of TOTAL BODY SURFACE AFFECTED	
HEAD		10%		
TRUNK		30%		
UPPER LIMBS		20%		
LOWER LIMBS		40%		
TOTAL		100%		
	HEAD TRUNK UPPER LIMBS LOWER LIMBS	AFFECTED HEAD TRUNK UPPER LIMBS LOWER LIMBS	AFFECTEDSURFACE AREAHEAD10%TRUNK30%UPPER LIMBS20%LOWER LIMBS40%	AFFECTEDSURFACE AREASURFACE AFFECTEDHEAD10%10%TRUNK30%10%UPPER LIMBS20%10%LOWER LIMBS40%10%

Row		Head	Trunk	Upper Limbs	Lower Limbs]
1	Erythema*					
2	Thickness*					
3	Scaling*					
4	Total each column					
5	Degree of Involvement**					
6	Multiply Row 4					na un a ĝoj
7		x 0.10	x 0.30	x 0.20	x 0.40	
8	Multiply Row 6 By Row 7				 	

.

Appendix B: PSORIASIS AREA SEVERITY INDEX (PASI)

*Rank severity of psoriatic lesions:

0 = none

ezene alerena j

- 1 = slight
- 2 = moderate
- 3 = severe
- 4 = very severe

**Rank area of psoriatic involvement:

0 = none

1

- 1 = <10%
- 2 = 10% to <30%
- 3 = 30% to <50%
- 4 = 50% to <70%
- 5 = 70% to <90%
- 6 = 90% to 100%

Appendix C: Subject Assessments of Pruritis (itching)

Subjects will be instructed to assess the level of the indicated symptom over the previous 24hour period using the following scale:

Rate the severity of pruritis (itching)

None

Appendix D: Dermatology Life Quality Index (DLQI)

٠.

। . .

Score:

The aim of this questionnaire is to measure how much your skin problem has affected your life OVER THE LAST WEEK. Please tick \square one box for each question.

	1.	Over the last week, how itchy, sore, painful or stinging has your skin been?	Very much A lot A little Not at all	
	2.	Over the last week, how embarrassed or self conscious have you been because of your skin?	Very much A lot A little Not at all	
sta s⊶dast jægs⊐ (530,151)	3.	Over the last week, how much has your skin interfered with you going shopping or looking after your home or garden?	Very much A lot A little Not at all	Not relevant 🗖
	4.	Over the last week, how much has your skin influenced the clothes you wear?	Very much A lot A little Not at all	Not relevant 🗖
	5.	Over the last week, how much has your skin affected any social or leisure activities?	Very much A lot A little Not at all	Not relevant 🗖
	6.	Over the last week, how much has your skin made it difficult for you to do any sport?	Very much A lot A little Not at all	Not relevant 🗖
	7.	Over the last week, has your skin prevented you from working or studying ?	Yes No	Not relevant 🗖
		If "No", over the last week how much has your skin been a problem at work or studying ?	A lot A little Not at all	
	8.	Over the last week, how much has your skin created problems with your partner or any of your close friends or relatives ?	Very much A lot A little Not at all	Not relevant 🗖

9.	Over the last week, how much has your skin caused any sexual difficulties?	Very much A lot A little Not at all	Not relevant 🗖
10.	Over the last week, how much of a problem has the treatment for your skin been, for example by making your home messy, or by taking up time?	Very much A lot A little Not at all	Not relevant 🗖

Please check you have answered EVERY question. Thank you.

۱ ۱

Source: Finlay, 1994.

ł

Appendix E:

Instructions: Please take some time to think about your level of satisfaction or dissatisfaction with the medication you are taking in this clinical trial. We are interested in your evaluation of the effectiveness, side effects, and convenience of the medication over the last two to three weeks, or since you last used it. For each question, please place a single check mark next to the response that most closely corresponds to your own experiences.

1. How satisfied or dissatisfied are you with the ability of the medication to prevent or treat your condition?

 \square_1 Extremely Dissatisfied \square_3 Dissatisfied \square_5 Satisfied □7 Extremely Satisfied □₂ Very Dissatisfied Somewhat Satisfied \square_6 Very Satisfied 2. How satisfied or dissatisfied are you with the way the medication relieves your symptoms? □₅ Satisfied □₃ Dissatisfied Extremely \Box_1 Extremely Dissatisfied \Box_7 Satisfied □₄ Somewhat Satisfied \square_6 Very Satisfied □₂ Very Dissatisfied 3. As a result of taking this medication, do you experience any side effects at all? \square_0 No \Box_1 Yes 4. How dissatisfied are you by side effects that interfere with your physical health and ability to function (e.g., strength, energy levels)? \square_1 A Great Deal \square_2 Ouite a Bit \square_3 Somewhat \square_4 Minimally □₅ Not at All 5. How dissatisfied are you by side effects that interfere with your mental function (e.g., ability to think clearly, stay awake)? \square_1 A Great Deal □ 2 Ouite a Bit \square_3 Somewhat \square_4 Minimally □₅ Not at All 6. How dissatisfied are you by side effects that interfere with your mood or emotions (e.g., anxiety/fear, sadness, irritation/anger)? \square_1 A Great Deal □₅ Not \square_4 Minimally \square_2 Quite a Bit Somewhat D٦ at All 7. How satisfied or dissatisfied are you with how easy the medication is to use? \square_3 Dissatisfied □₅ Satisfied □1 Extremely Dissatisfied \square_7 Extremely Satisfied □₂ Very Dissatisfied \square_4 Somewhat Satisfied \square_6 Very Satisfied 8. How satisfied or dissatisfied are you with how easy it is to plan when you will use the medication each time?

ΠI	Extremely Dissatisfied	\square_3	Dissatisfied	\square_5 Satisfied	D 7	Extremely
----	------------------------	-------------	--------------	-----------------------	------------	-----------

Satisfied

Calendaria da

\square_2 Very Dissatisfied	□4	Somewhat Satisfied	□6	Very Satisfied		
9. How satisfied or dissatisfied	are y	ou by how often you are	expe	cted to use/take the medie	cat	ion?
□1 Extremely Dissatisfied	□3	Dissatisfied		Satisfied C	7	Extremely
Satisfied □2 Very Dissatisfied	□4	Somewhat Satisfied	□6	Very Satisfied		
10. How satisfied are you that	the go	ood things about this med	licatio	on outweigh the bad thing	gs?	
□1 Extremely Dissatisfied Satisfied	□3	Dissatisfied	□5	Satisfied	37	Extremely
□ ₂ Very Dissatisfied						* · ·
11. Taking all things into acco	unt, h	ow satisfied or dissatisfie	ed are	you with this medication	1?	
□1 Extremely Dissatisfied Satisfied	□3	Dissatisfied	□5	Satisfied (37	Extremely

۱ ۱

Ξ.

 \square_2 Very Dissatisfied \square_4 Somewhat Satisfied \square_6 Very Satisfied

Atkinson et al., 2005

Appendix F: Washout for Psoriasis Medications

a. Topical immunomodulators, topical vitamin D derivatives, tar, salicylic acid, anthralin or any other topical treatment for psoriasis except topical corticosteroids that they are already using within 2 weeks of baseline.

b. Use of any biologics within 5 Half-lives of baseline and Ustekinumab use within 6 months
 c. Use of other systemic psoriasis treatments (ie, oral retinoids, methotrexate, cyclosporine, or other immunomodulators) within 4 weeks of baseline.

d. Use of UVB or PUVA within 2 weeks of baseline.

e. Use of any investigational drug within 4 weeks prior to randomization, or 5 pharmacokinetic/pharmacodynamic half lives, if known (whichever is longer)

Appendix G: Exploratory Cytokine Assays

Whole blood samples will be obtained with consent from patients participating in the clinical trial. Drugs used will include PDE7A inhibitor(s) alone or in combination with apremilast. Assays will include measurement of inflammatory cytokines following stimulation with LPS or anti-CD3

Methods: please draw one or two 10 mL heparin tubes per patient per visit (B, 8, 12) and label each tube as follows:

Pt. number

Pt. initials

Date sample taken

Timepoint of sample (Baseline, Wk 8, Wk 12)

Please have a note in the box stating that the shipment is from [name] ITT.

Ship tubes At ambient temperature promptly via overnight (FED EX) courier to Celgene San Diego for testing in ex vivo assays. The site will contact to alert prior to shipping the samples to the below address.

ال المراجع المراجع المراجع المراجع المراجع ومحمد ومعهم ومراجع المراجع المراجع المراجع المراجع المراجع المراجع المراجع ومراجع المراجع المراجع

Celgene San Diego Attn: [name] [name] Ph: [contact] [contact]

Work flow and brief description of whole blood assay: Whole blood samples from each patient, at each of the three clinical trial time points (baseline, week 8 and week 16) will be run immediately in the whole blood assay at Celgene labs

Compounds will be prepared, alone or as a combination, in triplicate as a 6-point dose, 1:3 dilution series starting at final concentration of 10uM. Whole-blood will be diluted 1:1 with warmed RPMI and pre-incubated with compounds for 1 hour in a tissue culture incubator. Compound-treated whole blood will then be transferred to a plate for stimulation with LPS or anti-CD3 and placed in tissue culture incubator for an additional 24 or 48 hours, repectively. The plates will then be spun down for 10 minutes, supernatant collected and frozen for later or transferred to directly to plates for analysis of specific cytokines including TNF- α , IFN- γ , IL-17 among others.

Outcomes: The study will seek to obtain in vitro evidence that a PDE7A inhibitor (or combination) can inhibit cytokine secretion in blood from patients being actively treated with

A

apremilast and determine how this inhibitory effect changes over length of treatment and across analytes. Because clinical assessments of disease will be collected throughout this study, it will be possible to compare these in vitro effects with clinical outcomes. Of note, inhibition of cytokine secretion does not always correlate with clinical efficacy.

1

and the second second

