Mean change and percent change in BSA (%) at wk 8 and wk 16 compared to baseline Proportion of patients who achieve PASI 50 at wk 8 and wk 16 Proportion of patients who achieve PASI 75 at wk 8 and wk 16 Percent of patients achieving 0 (clear) or 1 (almost clear) on patient global assessment scale at wk 8 and wk16 Reduction of topical use Satisfaction (TSQM, v2) at wk4, 8 and 16

Exploratory Objective:

The study will seek to obtain in vitro evidence that a PDE7A inhibitor (or combination) can inhibit cytokine secretion in blood from patients being actively treated with apremilast and determine how this inhibitory effect changes over length of treatment and across analytes.

Subject Characteristics

Subjects with moderate plaque-type psoriasis who are uncontrolled or dissatisfied on topical therapy (either 2 weeks use of high potency topical steroids or 4 weeks use of mid potency topical steroids) within the 6 months. "Uncontrolled" on topical therapy is defined as lack of efficacy per treating physician discretion and/or lack of patient-reported satisfaction on topical treatment.

Total number of subject is 20.

SELECTION AND WITHDRAWAL OF SUBJECTS

Inclusion Criteria

Subjects must satisfy the following criteria to be enrolled in the study:

- 1. Must be in general good health (except for disease under study) as judged by the Investigator, based on medical history, physical examination, clinical laboratories, and urinalysis. (NOTE: The definition of good health means a subject does not have uncontrolled significant co-morbid conditions).
- Females of childbearing potential (FCBP)[†] must have a negative pregnancy test at Screening and Baseline. While on investigational product and for at least 28 days after taking the last dose of investigational product, FCBP who engage in activity in which conception is possible must use one of the approved contraceptive§ options described below:

Option 1: Any one of the following highly effective methods: hormonal contraception (oral, injection, implant, transdermal patch, vaginal ring); intrauterine device (IUD); tubal ligation; or partner's vasectomy;

OR

Option 2: Male or female condom (latex condom or nonlatex condom NOT made out of natural [animal] membrane [for example, polyurethane]; PLUS one additional barrier method: (a) diaphragm with spermicide; (b) cervical cap with spermicide; or (c) contraceptive sponge with spermicide.

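### Exploratory cytokine assay: the time from last apremilast dose to blood draw is neither recorded nor kept consistent, so change over treatment cannot be separated from drug on board at the draw

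*Combined protocol and SAP*

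**What the plan says.** The Exploratory Objective, repeated in Appendix G, is to show inhibition of cytokine secretion in blood from patients on apremilast and to "determine how this inhibitory effect changes over length of treatment and across analytes". That is a within-patient comparison across visits.

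Appendix G describes the added compounds as follows: "Drugs used will include PDE7A inhibitor(s) alone or in combination with apremilast", and "Compounds will be prepared, alone or as a combination, in triplicate as a 6-point dose, 1:3 dilution series starting at final concentration of 10uM". On handling of the blood it says: "Whole-blood will be diluted 1:1 with warmed RPMI and pre-incubated with compounds for 1 hour in a tissue culture incubator". It mentions no wash step, no measurement of apremilast in the sample, and no reference well without compound.

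On timing, the visit lists under Study Procedures give tube type and volume only. The tube label asks for "Date sample taken" and the nominal visit, but no clock time and no time of last dose. Treatment Compliance asks about missed doses, not about when the last one was taken. Exclusion criterion 11 rules out prior apremilast, so baseline blood should contain none.

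Appendix G also disagrees with itself on the third sample. The label reads "Timepoint of sample (Baseline, Wk 8, Wk 12", while the work flow says samples "at each of the three clinical trial time points (baseline, week 8 and week 16) will be run immediately in the whole blood assay". Table 1 has no week 12 visit. These passages must be reconciled; the point below applies to either reading.

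**The concern.** The quantity of interest is a change in inhibition with length of treatment. What the wells contain at each visit depends on the added compound and on the apremilast circulating when the blood was drawn. The second part varies with hours since the last tablet, and the plan neither holds it steady nor records it.

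Two contrasts are affected in different ways:

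- **Week 8 versus final sample.** Both are on-treatment. If the draw-to-dose gap differs systematically between the visits, the contrast is biased. If it does not, the gap adds variability. Without times, these cases cannot be distinguished and no adjustment is possible.
- **Baseline versus either on-treatment sample.** Drug is absent, then present. Time on treatment is mixed with the acute presence of drug, whatever the draw time.

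At stake is the length-of-treatment half of the exploratory objective. The blood is run fresh, so missing times or omitted reference wells cannot be reliably recovered afterwards.

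**Working it through.** The plan gives no figure to reproduce for this assay. The dilution series comes from Appendix G. Half-life, blood level, IC50 and the spread of draw times are assumptions, because the documents give none of them. Dosing is referred to the label, so the dosing interval is not stated either.

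1. **Added concentrations.** 10/3^i for i = 0 to 5 gives 10, 3.33, 1.11, 0.370, 0.123 and 0.041 uM, a span of 3^5 = 243.

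2. **Circulating drug against time since dose.** The ratio is 2^(difference in hours / half-life). For a 12 h difference: half-life 6 h gives 2^2 = 4; half-life 12 h gives 2^1 = 2. In units of one 3-fold dilution step this is log 4/log 3 = 1.3 and log 2/log 3 = 0.6.

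3. **Carry-over into the well.** The 1:1 dilution halves the blood level. Assumed levels of 0.05, 0.2 and 1.0 uM at 1 h after a dose give 0.025, 0.10 and 0.50 uM in the well. Divided by 0.041 uM, that is 0.6, 2.4 and 12 times the lowest added concentration.

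4. **Can the readout move when the PDE7A effect does not?** Illustrative model: apremilast inhibition I(c) = 0.8c/(c + IC50) with IC50 = 0.1 uM; a constant 30% PDE7A effect acting multiplicatively; a = 0.37 uM apremilast added; b = in-well carry-over. Combination inhibition against the same-visit no-compound well is 1 − 0.7(1 − I(a+b))/(1 − I(b)).
   - Baseline, b = 0: I(0.37) = 0.630, so 1 − 0.7 × 0.370 = 74%.
   - 1 h after dose, b = 0.10: I(0.10) = 0.40 and I(0.47) = 0.660, so 1 − 0.7 × 0.340/0.60 = 60%.
   - 12 h after dose, b = 0.015 (half-life 4 h) to 0.053 (half-life 12 h): 72% to 66%.
   - Over IC50 0.03 to 0.3 uM, levels 0.05 to 1.0 uM and half-lives 4 to 12 h, the gap between 1 h and 12 h runs from about 1 to 24 percentage points.

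5. **Week 8 versus final sample** (level 0.2 uM, IC50 0.1 uM, half-life 4 to 12 h). If hours since dose are uniform on 1 to 12 h at both visits, the mean bias is 0 and the added per-patient SD is about 2 to 5 points. For a mean over all 20 subjects that is 2.3/√20 = 0.5 to 4.6/√20 = 1.0 points of standard error, and more if fewer consent. If the final draws shift to 6 to 12 h, the bias is about 1 to 3 points.

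6. **Which reference wells help.** In the same model, combination against apremilast alone at the same added concentration is 1 − 0.7(1 − I(a+b))/(1 − I(a+b)) = 30% at every visit. PDE7A alone against the same-visit no-compound well is also 30%. Both results depend on the two effects being multiplicative. If the drugs interact, on-board apremilast still matters, and the recorded interval is needed.

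**The case against.** The strongest reply has four parts.

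- **Apremilast in the blood is intended.** The objective concerns treated patients, and the stated concentrations describe added compound. This stands: the presence of drug is not an error. What is missing is a record of how long after a dose the blood was taken.
- **Untimed draws need not bias the on-treatment contrast.** This also stands. A reader might infer that length of treatment is wholly confounded with hours since dose. The documents do not support that, because nothing in them makes the gap differ between week 8 and the final visit. Collection of study drug at the final visit does not set it apart, since the visit lists also have collection at weeks 4 and 8.
- **Appendix G may already provide for apremilast alone.** A reader might infer from the drug list that no such series is planned and that the combination wells therefore cannot be interpreted. But the list is introduced as what the drugs will include, the dilution sentence has compounds prepared singly or combined, and the text is a summary of the assay. The layout is unclear; an omission is not shown.
- **The size is conditional.** A 2- to 4-fold difference is about one dilution step in a 243-fold series, and the modelled shifts rest on assumed pharmacology. This stands, and it limits the point's weight.

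None of this supplies the missing times.

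**Conclusion.** The concern holds in limited form. The plan studies change over treatment while leaving the draw-to-dose interval uncontrolled and unrecorded, and on-board apremilast is halved but not measured. For week 8 versus the final sample, the supported claim is extra variability that cannot be told apart from bias. In the base illustration (step 5) this is a per-patient SD of about 2 to 5 points, or a bias of about 1 to 3 points under one assumed shift. For baseline versus on-treatment, the main issue is drug absent versus present, which timing alone would not resolve. All sizes rest on the assumed half-life, blood level, IC50 and draw times.

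Severity is minor: the samples are optional, the objective is exploratory, at most 20 subjects contribute, and no primary or secondary endpoint is touched.

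**What to change.** - Add the clock time of the draw and the date and time of the last apremilast dose to the tube label and the CRF.
- Schedule each patient's assay draws at a similar time of day across visits, without changing dosing.
- State in Appendix G that every plate carries no-compound wells from the same draw and an apremilast-alone series beside the PDE7A and combination series, with inhibition expressed against the same-visit no-compound wells.
- Report change over treatment with the draw-to-dose interval examined, and do not attribute baseline versus on-treatment differences to treatment duration alone.
- Reconcile week 12 and week 16 for the third sample.

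Cost: two extra fields, some scheduling effort and more wells. Each series needs 6 points × 3 replicates × 2 stimuli = 36 wells. Three series need 108 wells, or 10.8 mL at an assumed 0.1 mL of blood per well. Triplicate no-compound wells for two stimuli add 6 wells, or 0.6 mL. The total of 11.4 mL would need the second 10 mL tube that Appendix G already allows.

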Appendix H: Patient Global Assessment (PtGA)

e Category Category Description			
Clear	No psoriasis symptoms at all		
Very mild	Very slight psoriasis symptoms, does not interfere with daily life		
Mild	Slight psoriasis symptoms, interferes with daily life only occasionally		
Moderate	Definite psoriasis symptoms, interferes with daily life frequently		
Severe	Intense psoriasis symptoms, interferes or restricts daily life very frequently		
	Clear Very mild Mild Moderate
